**Table 3 Additional Pregnancy Testing for Long-Term Extension**

LTE Trial Period	Visit Weeks During LTE Treatment Period																
	20	28	32	36	44	48	56	60	64	68	72	80	84	88	92	96	100
Trial Day	143	200	229	258	315	344	402	430	459	488	516	574	602	631	660	688	717
Visit	8a	9a	9b	9c	10a	10b	11a	11b	11c	11d	11e	12a	12b	12c	12d	12e	12f
Visit window (±day)	±3	±3	±3	±3	±3	±3	±3	±3	±3	±3	±3	±3	±3	±3	±3	±3	±3
Highly sensitive urine pregnancy test a	X	X	X	X	X	X	X	X	X	X	X	X	X	X	X	X	X

AE = adverse events, LTE = Long-Term Extension.

a In-between visit urine pregnancy test will be performed at home. The site staff will call the subject to confirm completion of the home pregnancy testing and discuss results. Any occurrence of pregnancy results in subject withdrawal from IMP and the trial (see Section 5.5.1 and 5.5.2).

## 2 Sponsor, Investigators and Trial Administrative Structure

The Sponsor of this clinical study is EMD Serono Research & Development Institute, Inc. (EMD Serono R&D), Billerica, MA, in the USA; Merck Serono Co., Ltd. (Affiliate of Merck KGaA, Darmstadt, Germany) in Japan; and Merck KGaA, Darmstadt, Germany, in rest of the world (RoW).

### Study Organization in Japan:

Refer to the Study Organization in Japan in the supporting documentation for additional information.

A contract research organization (CRO), PPD [REDACTED], will undertake the operational aspects of this study. In Japan, PPD [REDACTED], will undertake the operational aspects. Details of such structures and associated procedures will be defined in a separate Integrated Project Management Plan (IPMP). The IPMP will be prepared by the PPD [REDACTED] Clinical Project Manager in cooperation with other PPD [REDACTED] Operational Team Leads.

### 2.1 Investigational Sites

The study will be conducted in multiple centers, at approximately 180 sites, across approximately 20 countries.

Approximately 40 sites are anticipated to participate in the United States.

### Study sites in Japan:

Refer to the Study Sites in Japan in the supporting documentation for additional information.

### 2.2 Trial Coordination / Monitoring

The study will appear in the following clinical trial registry: [clinicaltrials.gov](http://clinicaltrials.gov).

The Sponsor will enlist the support of PPD [REDACTED], a CRO, to conduct the clinical part of the study including study set-up, operation of an interactive web response system (IWRS) for randomization, coordination, monitoring, medical oversight, data capture, data management, statistical analysis, and clinical study reporting. The Sponsor will also make use of the CRO's central laboratory for sample analyses, storage, and shipment to specialized bioanalytical laboratories. The Sponsor will supervise all outsourced activities.

Investigational medicinal product (IMP) will be supplied by the Clinical Trial Supply Department of the Sponsor, and packaged, labeled and distributed by a designated contract manufacturing organization.

The Coordinating Investigator PPD [REDACTED] represents all Investigators for decisions and discussions regarding this study, consistent with the

International Council for Harmonisation (ICH) Topic E6 Good Clinical Practice (GCP); hereafter referred to as ICH GCP. The Coordinating Investigator will provide expert medical input and advice relating to study design and execution and is responsible for the review and signoff of the clinical study report (CSR). Signature pages for the protocol lead and the Coordinating Investigator as well as a list of Sponsor responsible persons are in [Appendix IV](#).

Subject enrollment and randomization will be managed by an IWRS.

Safety laboratory assessments will be performed centrally. Use of local laboratories is optional and to be used at the discretion of the Investigator; however, duplicate samples must also be collected and sent for central laboratory analysis. Only central laboratory data will be transferred into the clinical database. Unless otherwise specified (see Section 7.4.3), local laboratory results will not be recorded in the electronic case report forms (eCRFs). Urinalysis will be performed locally; microscopic analysis and urine protein to creatinine ratio (UPCR) will be performed centrally.

CCI

The Global Drug Safety Department, Merck KGaA, Darmstadt, Germany, or their designated representatives will supervise drug safety and the timely reporting of adverse events (AEs), and serious adverse events (SAEs). Quality assurance of the study conduct will be performed by the Development Quality Assurance Department, Merck KGaA, Darmstadt, Germany.

The department of Global Biostatistics, Merck KGaA, Darmstadt, Germany, will supervise the statistical analyses, which will be outsourced to a CRO. Pharmacokinetic data analyses will be completed by Merck KGaA.

An independent data monitoring committee (IDMC) will be established to assess safety and tolerability of IMP during the conduct of the study and review the interim analysis (IA) if completed. The IDMC will be composed of a minimum of three members who do not have any conflict of interests with the study Sponsor, including two clinicians and a biostatistician. The full membership, mandate, and processes of the IDMC will be detailed in the IDMC charter. The IDMC will review the data from the interim futility analysis conducted by an independent third party statistician. Based on the pre-defined futility criteria, the IDMC will make recommendations to the Sponsor.

The IDMC will monitor the study until the last subject has either entered the LTE or completed the Safety Follow-Up Visit following the DBPC Treatment Period for subjects that did not rollover into the LTE, whichever occurs last. At that time, study monitoring may transition to an internal Safety Monitoring Committee (SMC). The SMC will review all available safety data on a regular basis during the open-label LTE. The SMC consists of Sponsor representatives (including, but not limited to, the Medical Responsible, the Drug Safety Product Lead, the biostatistician), the Medical Monitor from the CRO, and the Coordinating Investigator. The full membership, mandate, and processes of the SMC will be detailed in the SMC charter.

In addition, the trial will be advised and monitored by a Study Steering Committee. Details about this committee will be provided in a separate charter.

Details of structures and associated procedures will be defined in a separate Manual of Procedures, which will be prepared under the supervision of the Clinical Trial Leader.

CCI

CCI

B cell modulators have shown efficacy in several AIIDs. Belimumab, approved in 2011 in the US and EU for the treatment of lupus, inhibits B cell survival and differentiation into plasma cells (Benlysta® 2015). CCI

Rituximab has established efficacy (approved in the USA and EU) in RA and granulomatosis with polyangiitis/microscopic polyangiitis (Rituxan® 2016) and reported efficacy in a broad range of AIID disorders, including multiple sclerosis (Naismith 2010, Tanasescu 2014) and other autoimmune disorders (Kasperkiewicz 2011,

Lunardon 2012, Tony 2011, Xin 2013). In addition, other agents targeting B cells are in late stage development for systemic lupus erythematosus (SLE) (Furie 2014, Wallace 2014).

Although randomized controlled studies with rituximab in SLE and lupus nephritis have not demonstrated significant benefit over placebo (Borba 2014, Merrill 2010, Rovin 2012), this may be related in part to study design, as significant changes in background therapy were allowed. These results contrast with numerous uncontrolled studies and observational studies that have suggested benefit; many in the rheumatology community perceive rituximab to be effective for a number of manifestations of SLE, and this off-label use is recommended in SLE treatment guidelines as an alternative for the treatment of refractory lupus nephritis (Bertsias 2008, Hahn 2012, KDIGO 2012).CCI

CCI

CCI

CCI

The present Phase II study (MS200527-0018) is designed to determine the efficacy and safety of M2951 in subjects with SLE, and to determine a dose to take forward into Phase III development. Based on the available nonclinical and clinical data to date, the conduct of the study specified in this protocol is considered justifiable.

The available nonclinical and clinical data to date clearly support the pathogenic contribution of B cells in SLE. Novel non-depleting B cell therapies may deliver a more favorable benefit-risk balance than current B cell directed therapeutic approaches. In addition to silencing B cells, M2951 prevents innate immune cell activation which contributes to its efficacy. This is underlined by in-house preclinical data demonstrating superior efficacy over B cell depletion in a mouse lupus model, as well as efficacy in a mouse arthritis model despite continued presence of collagen-specific autoantibodies. CCI

CCI [Redacted]

CCI [Redacted]

CCI [Redacted] CCI [Redacted]

CCI [Redacted]

M2951 is being considered for the treatment of autoimmune diseases, including RA, SLE, and multiple sclerosis. To date, no efficacy data are available. However, because its mechanism of action directly targets both the production of autoantibodies and cellular effectors of end-organ injury, it is reasonable to anticipate that M2951 may represent a significant advance in the treatment of SLE and other autoimmune diseases.

### 3.1 Benefit and Risk

No identified risks or new potential risks have emerged from clinical studies thus far. In the first in human Study EMR200527-001, M2951 was well tolerated. CCI [REDACTED]  
[REDACTED] In the completed Phase Ib study in subjects with SLE (Study EMR200527-002) M2951 was well tolerated. There were no SAEs reported during the study and no new safety signals were identified. Evidence of clinical benefit was not expected in this 4-week safety study. CCI [REDACTED]  
[REDACTED]

Important potential risks to subjects are based on nonclinical safety data of M2951 and clinical data on adverse drug effects associated with compounds of a similar pharmacological class. They include infection, leukopenia, thrombocytopenia, hemorrhage, gastrointestinal intolerance, renal toxicity, hepatocellular injury, atrial fibrillation, drug-drug interactions, and embryo-fetal toxicity. Asymptomatic elevations in amylase and/or lipase have been observed in completed clinical studies of M2951. The clinical significance and risk status of these observations are being assessed. The Sponsor is also assessing the clinical significance of convulsions observed in dogs at very high levels of exposure.

Risk minimization measures inherent to early phase clinical trials are considered adequate for the proposed clinical trial in subjects with SLE. An IDMC will continually review available safety and tolerability data and will be mandated to make immediate decisions regarding the conduct of the trial; no additional risk minimization measures are proposed. During the LTE, an internal SMC may review safety data on a regular basis during the LTE in lieu of the IDMC.

CCI [REDACTED]

CCI [REDACTED]

CCI

Taking the above information into account, benefit-risk considerations support conduct of the proposed clinical trial MS200527-0018 in subjects with SLE.

CCI

CCI

Refer to the Investigator's Brochure for more details of each study. This clinical trial will be conducted in compliance with the CTP, ICH GCP, and any additional applicable regulatory requirements.

## 4 Trial Objectives

### 4.1 Primary Objectives

The primary objectives are:

- To evaluate the efficacy and dose response of M2951 compared to placebo in reducing disease activity in adult subjects with active, autoantibody-positive SLE who are receiving standard of care (SoC) therapy based on SLE Responder Index (SRI)-4 response at Week 52 in all subjects, or on SRI-6 response at Week 52 in the High Disease Activity (HDA) subgroup, defined as SLE Disease Activity Index 2000 (SLEDAI-2K)  $\geq 10$ .
- To evaluate the safety of M2951 in subjects with SLE on SoC therapy.

## 4.2 Secondary Objectives

The key secondary objectives are:

- To evaluate the efficacy and dose response of M2951 compared to placebo in delaying time to first severe flare during the Treatment Period, in subjects with SLE on SoC therapy, where a severe flare is defined as at least one British Isles Lupus Assessment Group (BILAG 2004) A in any organ system due to items that are new or worse, compared to the BILAG evaluation at the previous visit.
- To evaluate the efficacy and dose response of M2951 compared to placebo in reducing disease activity, based on the SRI-4 response at Week 52, in the serologically active subgroup, which is defined as subjects with positive anti-double-stranded deoxyribonucleic acid (anti-dsDNA) and/or low complement levels.

Other secondary objectives are:

- To evaluate the efficacy of M2951 compared to placebo on changes in disease activity over 52 weeks
- To evaluate the efficacy of M2951 compared to placebo on changes in organ-specific disease activity over 52 weeks
- To evaluate the effect of M2951 compared to placebo on the annualized flare rate
- To evaluate the impact of M2951 treatment compared to placebo on subject reported health related quality of life (HRQoL) over 52 weeks
- To evaluate the effect of M2951 on corticosteroid (CS) usage over 52 weeks.

CCI

CCI

## 4.4 Open-label Long-Term Extension (LTE) Period Objectives

The objective of the LTE Period is:

- To evaluate the long-term safety, efficacy, and HRQoL of M2951 at an initial dose of 50 mg twice daily or the eventual Phase III dose when decided for an additional two years.

## 5 Investigational Plan

### 5.1 Overall Trial Design and Plan

This is a Phase II, multicenter, international, randomized, double-blind, placebo-controlled (DBPC) parallel-arm trial, designed to determine the efficacy, dose response, and safety of M2951 in subjects with SLE, and to consider a dose to take forward into Phase III development.

Approximately 432 subjects are planned to be randomized in a ratio of 1:1:1:1 to receive one of three doses of M2951 (doses 25 mg once daily, 75 mg once daily, or 50 mg twice daily) or placebo, taken orally for 52 weeks. The study includes a Japanese cohort (approximately 36 Japanese subjects). If enrollment of Japanese subjects is slow, the entire Japanese cohort may not be part of the primary analysis. Therefore, the total enrollment will range from  $n = 432$  to 468 ( $n = 108$  to 117 subjects per group). All subjects that choose to enter the LTE Period will be switched to active treatment with M2951 [CCI] or to the eventual Phase III dose when decided. This trial will be conducted at approximately 180 sites across 20 countries.

The study is composed of a Screening Period of four weeks, a DBPC Treatment Period of 52 weeks, an open-label LTE Period of 104 weeks, and a Safety Follow-Up Period of four weeks.

The study will be conducted on an outpatient basis. Subjects will attend clinic visits at regular intervals as indicated in the Schedule of Assessments (SOA).

#### Screening Period

The first visit will be a Screening Visit and will include a review of the inclusion/exclusion criteria (see Section 5.3). Subjects should undergo the Day 1 Visit as soon as possible after eligibility for the study has been confirmed. During the Screening Period, there will be no change in oral corticosteroid (OCS) dose (see Section 6.4.2). Subjects who do not meet all inclusion criteria or meet an exclusion criterion within the Screening Period and are considered screen failures may undergo rescreening once, after approval by the Medical Monitor (see Section 7.1.1).

#### DBPC Treatment Period

Duration of the Treatment Period will be 52 weeks starting at randomization (Day 1). The Day 1 Visit will be considered the Baseline for disease activity (e.g., BILAG 2004, SLE Disease Activity Index-2000 [SLEDAI-2K], Physician's Global Assessment [PGA], and CLASI). Subject eligibility must be reviewed on Day 1 prior to randomization, and the first dose of the IMP (M2951 or placebo) will be given while the subject is still on site for Day 1. Subjects must then return to the study site for study visits as indicated in the SOA. Subjects will receive the last dose of IMP at Week 52, which is the EOT for the study, unless they enter the LTE Period.

From Day 1 to the Week 4 Visit, corticosteroids may be increased, decreased, initiated (within the first two weeks of the treatment period), or remain unchanged. However, the daily corticosteroid dose must be  $\leq 30$  mg/day prednisone-equivalent by the end of Week 4. From Week 4 to the Week 8 Study Visit, OCS dose will be reduced to establish a Threshold Dose, the maximum dose allowed during the remainder of the study, other than for treatment of flares. Treatment decisions will be made by Investigator assessment for the purpose of subject management. Rescue therapy will be allowed for the treatment of flares (see Section 6.4.2.2).

Any subjects permanently withdrawn from IMP will be expected to complete the EOT/Early Withdrawal study visit within five days of IMP withdrawal, followed by the Safety Follow-Up Visit four weeks post last dose.

### **Optional Open-Label Long-Term Extension Period**

Subjects who completed the 52-week DBPC Treatment period will be offered participation in the 104-week open-label, LTE Period of the study. The purpose of the LTE Period is to allow all the subjects with the opportunity to receive active treatment with M2951 and to collect long term safety and efficacy data. The Investigator should review the optional LTE Period with the subject prior to the DBPC Week 52 visit. Signed consent will be obtained prior to participation in the LTE Period. The DBPC Week 52/EOT Visit will be considered the LTE Day 1 Visit. The Safety Follow-Up Visit will be deferred until treatment is stopped in the LTE Period, due to either a subject's premature withdrawal/early termination from the LTE, termination of the study by the Sponsor, or completion of the LTE treatment period.

In some cases, due to Institutional Review Board (IRB)/Independent Ethics Committee (IEC) approval, regulatory-specific, or other administrative delays, a subject may experience a treatment gap between the IMP last dose received in the DBPC Period (Week 52/EOT visit) and the start of the LTE IMP treatment. Upon Principal Investigator (PI) request, these subjects may still be able to enroll in the LTE with approval from Merck/EMD Serono, on a case-by-case basis. If the day of rollover to the LTE occurs after the DBPC Week 56/EOS visit, all assessments noted at the LTE Day 1 visit will need to be completed. For subjects that rollover after the Week 52/EOT visit but prior to their scheduled Week 56/EOS visit, concomitant medications and AEs will need to be reviewed and updated, and the PI will need to ensure that the subject remains eligible for the study. No other additional assessments other than dispensing of IMP will need to be completed.

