- c Medical history includes documentation of SLE classification criteria, SLE medical history, medications, and surgery/procedures (see Section 7.2.1).
- d The results of a chest X-ray performed within three months prior to the Screening Visit (if available) are acceptable, provided there is no reason to suspect any clinical changes, per Investigator discretion.
- e Only required if change noted at Wk52/EOT, when compared to Baseline ECG.

- f Predose sample/procedure to be collected/performed before the first daily dose.
- g Abbreviated physical examination at these visits (see Section 7.4.4.2).
- h Abbreviated physical examination may be performed at Primary Investigator discretion, as required to fully obtain information needed for the BILAG and/or SLEDAI assessments, if scheduled, as well as required to fully evaluate any subject complaints or adverse events.
- i Vital signs include arterial BP, pulse rate, respiratory rate, and body temperature. Height will be measured at Screening only. Body weight will be measured with a balance beam scale, if possible. Pulse rate and BP will be measured after 10 minutes rest in the semisupine position with the subject's arm unconstrained by clothing or other material. The BP should be assessed on the same arm for each subject throughout the study.
- j Only CLASI assessed at Week 2.
- k On Study Visit Days, IMP should be administered during the Study Visit; otherwise, IMP should be self-administered at home at a set time each day (every 12 hours ± 2 hours). Investigational medicinal product administration at Week 52 will only occur for subjects rolling over into the LTE.
- l A Quantiferon test will be performed centrally. Prior TB testing results must be entered into the eCRF.
- m See Table 11 for list of clinical laboratory evaluations.
- n Supplementary LFTs include AST, ALT, alkaline phosphatase, GGT, and bilirubin.
- C** [REDACTED]
- C** [REDACTED]
- p To be collected at Screening only in subjects who have previously received B cell depleting therapy (see Exclusion Criterion 33, in Section 5.3.2).
- q HIV testing will be performed locally.

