Immunological Assessments															
Anti-dsDNA Complement (C3, C4), CRP	X									X		X		X	
ANA and other Autoantibodies	X									X		X		X	

ACR = American College of Rheumatology, ANA = Antinuclear Antibody(ies), Anti-dsDNA = Anti-Double-Stranded Deoxyribonucleic Acid, BILAG 2004 = British Isles Lupus Assessment Group 2004, CLASI = Cutaneous Lupus Erythematosus Disease Area and Severity Index, C-SSRS = Columbia-Suicide Severity Rating Scale, D = day, DNA = deoxyribonucleic acid, ECG = Electrocardiogram, EOT = End of Treatment, EQ-5D-5L = EuroQoL 5 Dimension 5 Levels, FACIT = Functional Assessment of Chronic Illness Therapy, HBsAg = hepatitis B surface antigen, HBV = Hepatitis B Virus, HRU = Health Resource Utilization, Ig = Immunoglobulin, IMP = Investigational Medicinal Product, LFT = liver function test, LTE = Long-Term Extension, LupusQoL = Lupus Quality of Life, PGA = Physician's Global Assessment, PGIC = Patient Global Impression of Change, CCI [REDACTED], SFI = SLEDAI Flare Index, SLEDAI-2K = Systemic Lupus Erythematosus Disease Activity Index-2000, SLICC = Systemic Lupus International Collaborating Clinics, SoA = Schedule of Assessments, UPCR = Urine Protein To Creatinine Ratio, Wk = Week, WOCPB = women of childbearing potential.

- a Safety Follow-Up Visits will be conducted at four weeks after the last dose of IMP for subjects who have been discontinued from IMP or have completed the LTE Treatment Period.
- b The LTE D1 visit is the EOT/Wk 52 visit from the DBPC Period unless a subject rollover more than four weeks after the Wk 52/EOT visit. If a subject exceeds the four weeks due to unanticipated causes (e.g., regulatory approval delay), prior approval from the Medical Monitor is required and the subject will need to complete the LTE D1 visit (see Section 7.1.3).
- c Vital signs including weight, oral temperature, seated blood pressure, pulse rate, and respiratory rate.
- d Only required if change noted at Wk 104/EOT, when compared to Baseline ECG.
- e Abbreviated physical examination may be performed at Primary Investigator discretion, as required to fully obtain information needed for the BILAG and/or SLEDAI assessments, if scheduled, as well as required to fully evaluate any subject complaints or adverse events (see Section 7.4.4.2).
- f [REDACTED]

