**Figure 3 Study Design for Long-Term Extension**

BID = twice daily, D = day, LTE = Long-Term Extension, QD = once daily, SFU = Safety Follow-Up, SLE = Systemic Lupus Erythematosus, WOCBP = women of child bearing potential.

\*\* = Subjects will receive an initial dose of 50 mg BID. When a Phase 3 dose is determined, all subjects may be switched to this dose at the Sponsor's discretion.

\* = For subjects entering the Open Label Extension, the Week 52 visit is considered the Day 1 visit for the Open Label LTE Period.

NOTE: For WOCBP, urine pregnancy tests will be performed at home to ensure monthly pregnancy testing.

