#### **7.4.3 Clinical Laboratory Assessments**

Blood and urine samples will be collected for the following clinical laboratory tests (Table 11), following the timing noted in the SOA (Table 1 and Table 2). All samples should be clearly identified. Sample collection, preparation, and handling/shipment procedures are described in the laboratory manual. For WOCBP, including those who are postmenopausal for less than 12 months, serum pregnancy tests will be performed at initial Screening, and high sensitivity urine pregnancy

tests will be performed at the visits specified in Table 1 and Table 3. Pregnancy tests will be done whenever 1 menstrual cycle is missed during the active treatment period, when potential pregnancy is otherwise suspected, and at the end of the study to confirm the subject has not become pregnant during the study. Pregnancy tests may be repeated per request of institutional review boards (IRBs)/ethics committees (ECs) or if required by local regulations.

Additional laboratory tests may be performed after abnormal findings. Local safety testing as requested by the study team should be entered into the eCRF.

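### Rollover into the LTE 1 to 27 days after Week 52 needs no pregnancy test before the first LTE dose, and the early liver checks stay dated from Week 52 instead of from that dose

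*Protocol*

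**What the plan says.** The rule stands in the Protocol synopsis and in Section 5.1, both under Optional Open-Label Long-Term Extension Period. The starting point is "The DBPC Week 52/EOT Visit will be considered the LTE Day 1 Visit". A gap before LTE dosing is then foreseen for ethics, regulatory or administrative delays, with sponsor approval case by case. Two branches follow.

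- Rollover after the Week 56 visit: all LTE Day 1 assessments are done. In Table 2 these include a urine pregnancy test, hematology and chemistry.
- Rollover after Week 52 but before the scheduled Week 56 visit: medications and adverse events are updated and the investigator confirms eligibility. Beyond that, "No other additional assessments other than dispensing of IMP will need to be completed".

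For the second group LTE Day 1 does not move. Table 2, footnote b, keeps it at Week 52 "unless a subject rollover more than four weeks after the Wk 52/EOT visit", and the note to Figure 3 repeats that "the Week 52 visit is considered the Day 1 visit for the Open Label LTE Period".

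At double-blind Day 1 the urine pregnancy test carries Table 1 footnote f: "Predose sample/procedure to be collected/performed before the first daily dose". Between scheduled visits, Section 7.4.3 provides that "Pregnancy tests will be done whenever 1 menstrual cycle is missed during the active treatment period", and also whenever pregnancy is otherwise suspected. Section 3.1 lists among the important potential risks "hepatocellular injury, atrial fibrillation, drug-drug interactions, and embryo-fetal toxicity".

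**The concern.** The abbreviated branch is an explicit waiver, not a silence that a manual could fill. It is the only route to a first dose, in either period, without a pregnancy test at that contact. A subject who rolls over on time has the Week 52 test at the same visit, and one who rolls over after Week 56 repeats it. The missed-cycle trigger is tied to active treatment, so it does not clearly cover the weeks off drug.

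The second consequence concerns liver monitoring. Table 2 places liver tests every two weeks up to Week 16. If visits are counted from Week 52 while dosing starts later, that run of tests moves towards, and partly ahead of, first exposure. The stake is highest for former placebo subjects, who start M2951 here at 50 mg twice daily. The hold-and-recheck rules for AST, ALT and bilirubin in Section 5.5.2 work only on blood drawn while the subject is on drug.

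**Working it through.** No stated figure needs reproducing; this is day arithmetic.

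**Inputs.** Table 1: Week 52 is Trial Day 365 and Week 56 is Trial Day 393. Table 2: AST and ALT are measured at LTE Weeks 2, 6, 10, 14 and 16 (supplementary liver tests) and Weeks 4, 8, 12 and 24 (routine chemistry). Windows are ±3 days up to Week 16. The first scheduled pregnancy test after LTE Day 1 is at Week 4.

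**Range of gaps.** 393 − 365 = 28 days, so rollover before the scheduled Week 56 visit means a gap g of 1 to 27 days.

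**Visit position.** The first LTE dose falls on LTE Day 1 + g. A visit on LTE Day d falls d − 1 − g days after it, which is 7 × week − g.

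| Gap g (days) | Week 2 | Week 4 | Week 16 | Week 24 | Days on drug to next scheduled pregnancy test (28 − g) |
|---|---|---|---|---|---|
| 0 | 14 | 28 | 112 | 168 | 28 |
| 7 | 7 | 21 | 105 | 161 | 21 |
| 14 | 0 | 14 | 98 | 154 | 14 |
| 18 | −4 | 10 | 94 | 150 | 10 |
| 21 | −7 | 7 | 91 | 147 | 7 |
| 27 | −13 | 1 | 85 | 141 | 1 |

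Columns 2 to 5 are days after the first LTE dose; a negative value is before it.

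- **Week 2 liver test:** 14 − g is 0 at g = 14 and negative from g = 15. The window ends at 17 − g, which is negative from g = 18, so from then on the whole window is past.
- **Checks on on-drug days 1 to 112:** 8 without a gap, 8 for g = 1 to 13, and 7 for g = 14 to 27.
- **First on-drug check, nominal date:** 14 − g for g = 1 to 13 (day 13 down to day 1), then 28 − g for g = 14 to 27 (day 14 down to day 1). It is never after day 14. At g = 26 or 27 an early-window Week 4 draw could precede first dose; the next check is then Week 6, at day 16 or 15.
- **End of two-weekly checks:** 112 − g, which is 98 at g = 14 and 85 at g = 27. The next check is at 168 − g, day 154 to 141.
- **Age of the last pregnancy test at first dose:** g, so up to 27 days.
- **Interval between scheduled pregnancy tests:** 28 days if visits stay dated from Week 52. If they were re-dated with no test at dispensing, it would be 28 + g, up to 55 days.

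**The case against.** The case for leaving the rule alone has four parts.

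1. **Dating is inferred.** No sentence says that later visits are not re-dated, and the Week 52 wording could mean only that its assessments serve as Day 1. The synopsis gives 104 weeks of LTE drug, whereas counting from Week 52 leaves a 27-day-gap subject 728 − 27 = 701 days, about 100 weeks. This stands in part. Keeping LTE Day 1 at Week 52 is the natural reading of Section 5.1, footnote b and the Table 2 day count, and nothing re-dates the visits. On the other reading the liver point disappears, but the pregnancy-test interval grows to as much as 55 days.

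2. **Little liver monitoring is lost.** This stands. Only Week 2 nominally falls on or before first dose, and unscheduled visits remain available.

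3. **Pregnancy testing keeps its four-week rhythm.** This also stands on the Week 52 dating. Two contraceptive methods are required until 90 days after the last dose (Section 5.3.1), suspicion triggers a test, and the eligibility check implies that the subject is not pregnant. No test has to support that check, however.

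4. **Stale safety labs are not a fault.** A reader might infer that the first LTE dose rests on outdated hematology and chemistry and that a repeat draw is needed. The Protocol does not support that. Week 52 is a full safety visit, and its results are at most 27 days old. An on-time subject is dosed during the Week 52 visit (Table 1, footnote k) while samples go to a central laboratory (Section 2.2), and no text makes that dose wait for results. The last results in hand may then be from Week 48, (52 − 48) × 7 = 28 days earlier.

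**Conclusion.** The point holds as a minor design weakness. For a gap of 1 to 27 days the stated rule gives less protection at first dose than the Protocol itself requires at double-blind Day 1 and after Week 56, for an embryo-fetal risk that it names. The early liver tests also stop tracking exposure: Week 2 is lost as an on-drug check from a 14-day gap, and the two-weekly run ends 14 to 27 days early for gaps of 14 to 27 days.

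A reader might infer that the Protocol contradicts itself here, or that liver safety goes unmonitored after a late rollover. Neither follows. The two branches are consistent with each other, and seven or eight liver checks remain in the first 112 on-drug days.

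The conclusion assumes that LTE visits stay dated from Week 52, which is the natural reading but is not separately stated. The pregnancy-test point does not depend on that assumption. The number of subjects affected is not given, and late rollover is a sponsor-approved exception. The primary analysis is not touched.

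**What to change.** Make two changes together.

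1. In the synopsis and Section 5.1, require a negative urine pregnancy test before the first LTE dose for any woman of childbearing potential who was not dosed at the Week 52 visit.
2. In Table 2, footnote b, date the Table 2 and Table 3 visits from the first LTE dose for subjects with a gap, and carry the same exception into the Figure 3 note. The Week 52 assessments can still serve as the LTE Day 1 assessments; only the visit calendar moves.

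The second change must not be made alone, because it would stretch the pregnancy-test interval to as much as 55 days. With both, the test is current at first dose, the next follows 28 days later, and liver checks return to on-drug days 14, 28 and so on up to 112.

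The cost is one urine test at a dispensing contact that already takes place, plus the wording. No repeat hematology or chemistry draw is needed, and nothing changes for subjects dosed at Week 52.
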